4. PROTOCOL SUMMARY

Title:	Magnetically Controlled Capsule For Assessment Of Gastric Mucosa In Symptomatic Patients: “MAGNET”
Précis:	This is a single-center prospective study examining the diagnostic utility of a single-use ingestible magnetically controlled capsule (MCC) endoscope (NaviCam™, AnX Robotica) which is remotely controlled by external hardware and software to visualize the mucosa of the stomach on patients with upper abdominal symptoms. Participants will be enrolled and tested at a central site referred from Emergency Departments (EDs), urgent cares (UCs) and primary care practices (PCPs) in the Washington, DC area and additional site(s) to be named. Total enrollment is estimated to be 72 patients with a goal of following all patients with a traditional endoscopy to confirm findings. Aim 1 is to establish feasibility of this novel outpatient testing. Aim 2 is to demonstrate high-quality visualization of gastric anatomic landmarks. Aim 3 is a pilot study to compare visualization of gastric anatomic landmarks and lesions of MCC follow-up traditional EGD. We currently anticipate enrolling 2-3 patients per week over 30 weeks.
Objectives:	
Aim 1: We aim to demonstrate feasibility of MCC in an outpatient primary and urgent care setting. Measured outcomes include duration of MCC test, linkage with EGD follow-up, image storage, image transfer, technician learning curve and documentation.
 
Aim 2: We aim to show that MCC can identify and photograph regions of stomach consistent with established visualized scoring systems for anatomic landmarks.
 
Aim 3: Pilot assessment of MCC compared to subsequent EGD to detect anatomic regions and gastric mucosal lesions.

Population:	An unselected pool of adult patients with an appropriate indication for upper endoscopy such as epigastric pain/burning, nausea and or vomiting, bloating, heartburn, iron deficiency anemia, unintended weight loss, abnormal imaging suggesting organic disease. In general, participants will be age ≥ 18 , mixed gender, mixed race, hemodynamically stable with possible co-morbidities.
Site Number	1
Study Duration:	Time needed to reach sufficient study subjects plus additional time for analysis
Subject Duration:	30 days
Estimated Time to Complete:	12 months

5. SCHEMATIC OF STUDY DESIGN:

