MCC offers potential advantages over traditional EGD including the ability to be performed 24 hours a day without sedation and to be performed by a clinician. In addition, the MCC is less invasive, does not cause discomfort, and enables the patient to pursue normal daily activities after the procedure. Non-specialist physicians can administer the MCC and interpretation can be done in real-time or asynchronously by GI specialists. The MCC may impact decisions regarding the need for hospitalization, the need for additional diagnostic testing such as biopsy, the need for additional therapeutic interventions such as endoscopic hemostasis and polypectomy, and the need for further risk stratification of disease. The eventual work-flow may be similar to that of many current diagnostic tests such as radiologic examinations. This ability to transmit images could become especially important in rural communities or in communities that have limited access to a gastroenterologist or surgeon. Incorporation of the MCC into current practice could follow a trajectory similar to that of point-of-care ultrasonography, an imaging modality in which non-radiologist physicians have become increasingly skilled and for which indications continue to expand (Bennet 2018). The American Society of Gastrointestinal Endoscopy states that credentials for capsule endoscopy should be determined independently from other endoscopic procedures such as colonoscopy, sigmoidoscopy, or any other endoscopic procedure (ASGE 2005). The American Society for Gastrointestinal Endoscopy also emphasizes that sound medical training, appropriate patient selection, correct interpretation, and continued medical management for all patients. Capsule endoscopy requires only image interpretation and does not require procedural skill training associated with other

endoscopic procedures; therefore, ED physicians, urgent care physicians and primary care doctors and mid-level practitioners can meet these criteria with basic training.

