8.3.3. Fasting and MCC prep

- NPO Midnight the day before MCC.

8.3.4. Scoring Anatomic Regions.

After confirming that gastric emptying has been achieved with overnight fast -- we will use the 5-point visualization score described in Ching, 2019 for the following anatomic regions

- Lower Esophagus / Z line
- Corpus
 - Greater curvature
 - Lesser Curvature
- Anterior Wall
- Posterior Wall
- Proximal stomach
 - Cardia/Fundus
- Distal Stomach
 - Antrum/Pylorus/Angularis
- Duodenum
 - Bulb
 - Ampulla

8.3.5. Scoring Gastric Mucosal lesions.

("yes/no")

- Visible Lesions (Paris Classification if relevant)
- Ulcers (+/- Forrest Classification)
- Gastric Atrophy
- Gastric Varices
- Gastritis*
- Hiatus hernia
- Submucosal lesions
- Plus: Does patient need endoscopic intervention?

8.3.6. Lesions picked up by MCC and not by EGD.

- Healing lesions (especially ulcers) are natural course of disease therefore we assume that some

lesions will be detected by capsule but not by EGD if EGD is done a few days later. With photo-documentation and two independent readers, we hope to assure that this phenomenon is a natural course of lesion and not a "false-positive" by MCC.

8.3.7. Measuring patient satisfaction (see *MAGNET7 and 8, day 7 and 30*).

- I felt the research team answered all my questions. Yes No
- Did you feel any pain with swallowing? Yes No
- How difficult was it to swallow the capsule? Very Easy Moderately Easy Neutral Moderately Difficult Very Difficult
- Did you feel discomfort after swallowing while operator moved the capsule? Yes No
- Did you notice the capsule pass during a bowel movement?? Yes No
- Any other issues? Yes No
- If yes, what were the issues? _____
- How much time in total approximately did you have to take out during your day for the capsule endoscopy procedure? _____ (we do not ask this)
- Did you feel like you needed to miss work after the capsule endoscopy procedure? Yes No (we do not ask this)
- Did you need someone to take you home after the capsule endoscopy procedure? Yes No (we do not ask this) In the future, if both studies were equally accurate and you needed another examination of your stomach, would you prefer to have a traditional EGD or a capsule? EGD Capsule. Why?

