will be pre-determined, and each area will have a predetermined number of images obtained as suggested by Gastroenterology Society guidelines.

5. Patient data collected will include the following elements: chief complaint of patient, history of present illness, past medical history, current medications (only PPIs and pain medication)..
6. At completion of MCC, video will be archived and patient satisfaction will be assessed. Capsule endoscopy will NOT be used for clinical decisions.
7. Patients will be instructed to return to the physician sooner, if concerning signs develop. A 7 and 30-day follow-up call and chart review is only performed if person is lost to follow-up will be conducted to check for symptom resolution and adverse events.
8. Esophagogastroduodenoscopy (EGD) will be performed as soon as possible in an appropriate endoscopy facility by an experienced endoscopist.
9. Endoscopic images will be stored in secure serve for later comparison with MCC images.

Summary of Research Strategy

- ❖ PRE-SCREEN (DAY -7 to DAY -1)
 - Upper Abdominal Pain or Related Symptoms (Indications for an EGD)
 - Performed in ED, UC, PCP offices or GI clinic
- ❖ SCREEN (DAY -7 -> DAY 0)
 - More thorough screening questions and scheduling by RC (<24 hours)
 - Performed by Telephone
- ❖ ENROLL (DAY 0)
 - Signed Informed Consent procedure, more detailed questions and MCC Procedure performed
 - Occurs at the GWU Medical Faculty Associates Building on [name].
 - NaviCam MCC performed by trained Clinician.
 - Reviewed by a Gastroenterologist.
 - Scheduled for an EGD will ideally be performed within 5 days of the MCC procedure, but will allow MCC procedure to be performed up to 14 days either before or after an EGD (paid by insurance as standard of care).
- ❖ FOLLOW-UP (DAY 1-30)

- Day 7 and Day 30: Telephone Call plus CRISP Chart Review, only if lost to follow-up.

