10. STUDY ENROLLMENT AND WITHDRAWAL

10.1. Subject Inclusion Criteria

1. Individuals aged \geq 18 years with upper GI symptoms (epigastric pain, bloating, burning, heart-burn, excessive belching, nausea and/or, vomiting, anemia, and weight loss) appropriate for an upper endoscopy evaluation.
2. Able to speak English
3. Able to understand and sign consent form
4. Able to undergo standard outpatient endoscopy
5. Indications for EGD Low blood (unexplained anemia)
 - Blood in vomit (hematemesis)
 - Upper abdominal or chest pain
 - Indigestion (dyspepsia)
 - GERD
 - Suspected ulcer
 - Unexplained weight loss
 - Gastric biopsy
 - Other

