13. HYPOTHESIS AND ANALYSIS

13.1. Study Hypothesis

Aim 1: We hypothesize that initiation of MCC pilot study will be feasible defined by outcomes related to (A) implementation, (B) Practicality and (C) Integration.

Aim 2: We hypothesize that MCC will meet established quality measures ($\geq 90\%$) for visualization of stomach anatomy landmarks.

Aim 3: We hypothesize that the MCC will be similar to EGD at visualization of gastric lesions and/or disease.

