13.2. Sample Size Considerations

The sample size for this Proof of Concept study was not chosen for statistical consideration, as there are no formal statistical inferences planned. The size of the study is judged adequate for the preliminary evaluation objectives. All 72 participants will receive the MCC and will be referred to follow-up EGD. The base-line prevalence of lesions and the estimated loss to follow-up will provide information for formal sample size calculation for follow-up study.

We did not use a statistical justification but a practical justification to choose 72 participants. All 72 will get the MCC unless they are unable to tolerate the capsule. The issue of drop-out is relevant only to Aim 3 which pilots the concept of non-inferiority compared to subsequent EGD. We did not power this study to prove non-inferiority --- this study will allow us to estimate baseline lesion prevalence and the likely drop-out rate. Moving forward, we will be able to calculate an accurate sample size for a future larger definitive non-inferiority study.

For patients in whom visualization is limited by incomplete gastric emptying, we will record fasting time but exclude patient from assessment of MCC accuracy.

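### The protocol lets the capsule follow the EGD by up to 14 days, while Aim 3 presumes a later EGD; biopsy or treatment at a prior EGD can create lesion discordance unrelated to the capsule

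*Protocol*

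**What the plan says.** **Order permitted.** The research-strategy summary in Section 9.4 aims for an EGD within 5 days of the capsule but "will allow MCC procedure to be performed up to 14 days either before or after an EGD". Step 3 of the same section has the coordinator book an EGD only where none is already booked, so EGD-first participants are a practical possibility.

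**Order presumed elsewhere.** Section 4 describes Aim 3 as "Pilot assessment of MCC compared to subsequent EGD to detect anatomic regions and gastric mucosal lesions". Section 13.2 says that Aim 3 "pilots the concept of non-inferiority compared to subsequent EGD" and that "All 72 participants will receive the MCC and will be referred to follow-up EGD". Item 8 of the Aim 3 list in Section 8.1 asks the capsule reader whether a follow-up EGD is needed.

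**Interval change.** The only provision is in Section 8.3.6, which expects that some "lesions will be detected by capsule but not by EGD if EGD is done a few days later".

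**Nature of the EGD.** It is standard of care and billed to the insurer (Sections 6.3.1 and 9.4). No limit on biopsy or treatment is stated. Section 10.1 lists "Gastric biopsy" among the indications.

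**Outcomes touched.** The Aim 3 hypothesis in Section 13.1 reads "We hypothesize that the MCC will be similar to EGD at visualization of gastric lesions and/or disease". Secondary outcome 4 in Section 8.2 compares sensitivity and specificity with earlier non-US trials for ulcers, cancer and inflammatory changes. The only stated exclusion from the accuracy assessment is incomplete gastric emptying (Section 13.2).

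**The concern.** For lesion scoring, the two orders are not equivalent. The capsule takes images only; Section 6.1 leaves capsule biopsy and therapy to future technology. Section 9.4 also bars capsule results from guiding care. Neither limit applies to the EGD, so the EGD can change what a later capsule sees, but the capsule does not change what a later EGD sees.

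If the EGD comes first, a lesion that is removed, or that resolves under treatment started on the EGD result, may be scored as present on EGD and absent on the capsule. A fresh biopsy or resection site may be scored by the capsule as an erosion or ulcer that the EGD did not have. Both are discordances caused by the reference procedure. Section 8.3.6 gives a reader only two explanations for a capsule-only lesion, natural healing or a capsule false positive, and neither fits a biopsy site.

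At stake are the Aim 3 lesion agreement and secondary outcome 4. Section 20 also lists a paper on non-inferiority for gastric lesions.

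**Working it through.** **1. Setting the text side by side.**

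| Place | Order |
|---|---|
| Section 9.4, strategy summary | either, up to 14 days apart |
| Section 4, Aim 3 | MCC, then EGD |
| Section 8.1, Aim 3 item 8 | MCC, then EGD |
| Section 8.3.6 | MCC, then EGD |
| Section 13.2 | MCC, then EGD |

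No section says how an EGD-first pair is handled in the lesion comparison. This conflict stands without any arithmetic.

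**2. No figure to reproduce.** Section 13.2 calls the 72 participants a practical choice and gives no power, margin or precision. What follows is illustration.

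**3. Cost of one altered lesion.** With D EGD-positive participants, one altered lesion that the capsule would have seen costs 100/D points of sensitivity. With 72 − D lesion-free participants, one biopsy site scored as a lesion costs 100/(72 − D) points of specificity. The protocol does not give D for this population. Its own figures allow a range:

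- Section 6.2: as many as 70% of EGDs without alarm symptoms are negative. 0.30 × 72 = 21.6, so D ≈ 22. Sensitivity: 1/22 = 4.5 points. Specificity: 1/50 = 2.0 points.
- Section 6.3.1, the 68-patient comparison: positive agreement 96.0%, negative 77.8%, overall 91.2%. These fit 48/50, 14/18 and 62/68, so 50/68 = 73.5% were gastroscopy-positive. 0.735 × 72 = 52.9, so D ≈ 53. Sensitivity: 1/53 = 1.9 points. Specificity: 1/19 = 5.3 points.

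If it is unknown whether the capsule would have seen the lesion, the first figure is multiplied by the cited sensitivity: 0.904/22 = 4.1 points.

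**4. Scenarios.** Let f be the share of EGD-first participants, r the share of lesions altered at EGD, and b the share of lesion-free participants with a biopsy mark that the capsule scores as a lesion. All three are assumptions. Start from Se = 90.4% and Sp = 94.7%, cited in Section 6.3.1:

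- apparent Se = Se(1 − fr) + (1 − Sp)fr
- apparent Sp = Sp(1 − fb)

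| f | r = b | Apparent Se | Apparent Sp |
|---|---|---|---|
| 0 | any | 90.4% | 94.7% |
| 25% | 10% | 88.3% | 92.3% |
| 25% | 30% | 84.0% | 87.6% |
| 50% | 10% | 86.1% | 90.0% |
| 50% | 30% | 77.6% | 80.5% |

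For the last row, fr = 0.15: 0.904 × 0.85 + 0.053 × 0.15 = 0.776, and 0.947 × 0.85 = 0.805. The spread reflects the chosen f, r and b. The table shows the direction of the bias, and that it vanishes at f = 0; it does not estimate what this trial will see.

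**The case against.** The strongest reply is that Aim 3 is already defined against a subsequent EGD, so read literally it is the MCC-first comparison. A reader might infer from Section 9.4 that both orders are pooled, but no section says so. That stands, and it makes the defect a conflict between Section 9.4 and Sections 4 and 13.2, with EGD-first pairs left unassigned.

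Four further limits also stand:

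- A reader might infer that the bias would carry into the sample size of the definitive study. Section 13.2 names lesion prevalence and drop-out as the inputs, not sensitivity or specificity.
- A reader might take Section 6.1 as saying that hemostasis and polypectomy are done at the study EGD. It mentions "the need for additional therapeutic interventions such as endoscopic hemostasis and polypectomy" among decisions the capsule may one day inform. The support for tissue alteration is the unrestricted standard-of-care EGD and the biopsy indication.
- Not every scored item is exposed. A biopsy would not ordinarily erase atrophy, varices or a hiatus hernia. A removed polyp belongs to the visible-lesion agreement, not to secondary outcome 4.
- The 70% figure applies without alarm symptoms, whereas Section 10.1 admits anemia, weight loss and hematemesis.

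It can also be said that an SAP or the EGD form, neither shown, may deal with test order, and that stored images and two independent readers may reveal a biopsy site. That is possible. But the conflicting order is fixed in the protocol itself, and sites not recorded at the EGD may be hard to recover later.

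**Conclusion.** The point holds as a conflict over test order with a plausible route to bias. EGD-first pairs are allowed, are not excluded from the lesion comparison, and can carry discordance produced by the EGD. The conclusion rests on an EGD without stated limits on biopsy or treatment; the protocol does not say that lesions will be altered, only that nothing prevents it.

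The total size cannot be derived. Each altered lesion that the capsule would have seen costs about 4.5 points of sensitivity if 22 of 72 are positive, and about 1.9 points if 53 are. A reader might go on to expect a loss of 5 to 14 points from one to three such cases, but the documents give no basis for that count.

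The effect is confined to Aim 3 lesion agreement and secondary outcome 4. Feasibility and landmark visualization by the capsule are largely untouched, and Section 13.2 plans no formal inference. The point should be corrected, but it does not threaten the study as a whole.

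**What to change.** - Reconcile Section 9.4 with Sections 4 and 13.2 by stating in Sections 8.1 and 13.1 that the main Aim 3 lesion comparison, and secondary outcome 4, use pairs in which MCC preceded EGD.
- Report EGD-first pairs separately, with their number.
- Record on the EGD form (Magnet 6), if it does not already do so, any site biopsied, resected or treated. In EGD-first pairs, do not count such a site as a capsule miss or false positive.
- Extend Section 8.3.6 to name this source of discordance.
- Keep all participants for landmark visualization by the capsule.

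The cost is a sentence or two and one form field. The main lesion comparison loses as many pairs as there are EGD-first participants. No stated power is affected, no procedure needs rescheduling and clinical care is unchanged.

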10. STUDY ENROLLMENT AND WITHDRAWAL

10.1. Subject Inclusion Criteria

1. Individuals aged \geq 18 years with upper GI symptoms (epigastric pain, bloating, burning, heart-burn, excessive belching, nausea and/or, vomiting, anemia, and weight loss) appropriate for an upper endoscopy evaluation.
2. Able to speak English
3. Able to understand and sign consent form
4. Able to undergo standard outpatient endoscopy
5. Indications for EGD Low blood (unexplained anemia)
 - Blood in vomit (hematemesis)
 - Upper abdominal or chest pain
 - Indigestion (dyspepsia)
 - GERD
 - Suspected ulcer
 - Unexplained weight loss
 - Gastric biopsy
 - Other

10.2. Subject Exclusion Criteria

Individuals with one or more of the following will not be eligible for participation in the study:

1. Hemodynamic shock
2. Active hematemesis
3. Dysphagia, swallowing disorder
4. Suspected bowel obstruction or perforation
5. Gastroparesis
6. Crohn's disease
7. Prior GI tract surgery that changes the gastrointestinal anatomy (e.g., Billroth I or II, esophagectomy, gastrectomy, bariatric procedure and small intestinal resection)
8. Presumed pregnant, trying to conceive or currently breastfeeding
9. Altered mental status (e.g., hepatic encephalopathy) that limits the ability to swallow a capsule
10. Expected to have Magnetic Resonance Imaging examination within 30 days.
11. No reliable contact information – no phone, no permanent address.
12. Pacemaker or ICD

13. BMI \geq 38

10.3. Strategies for Recruitment and Retention

Email notifications will be sent to GW providers on the study to help recruit eligible patients at GW EDs, urgent care facilities and PCP offices. Existing RA's stationed in those units will help spread the word about potential eligibility (i.e. stable for outpatient work-up, symptoms related to UGI tract.) Pre-screening will take place onsite. Full consent and interview for inclusion and exclusion criteria will occur by lead RC and PI at site of NaviCam.

10.4. Subject Withdrawal

10.4.1. Reasons for Withdrawal

A subject can withdraw at any time and for any reason. Subject should provide written notice to PI as to withdrawal intent. The PI can withdraw a patient from the study for noncompliance issues or serious medical conflicts.

10.4.2. Handling of Subject Withdrawals

If subject withdraws from the study, no further contact will be attempted or made by study staff. If patient is withdrawn from study by PI for non-compliance or health related concerns, study staff will notify subject via phone call and/or IRB approved letter, if direct contact cannot be made.

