The physical risks associated with the NaviCam MCC are generally related to potential non-natural excretion. There is a small risk that the capsule could become stuck in the stomach or small intestine. Based on published and unpublished data of other types of capsule endoscopes, retained capsules have persisted in the GI tract for periods for many years without adverse event. In fact, a large retrospective review by Cheifetz, et al. found that a retained capsule is often asymptomatic or leads to a diagnosis. (Chifetz 2006). Furthermore, the device is made of biocompatible materials and its internal parts are non-toxic. The incidence of capsule retention has been reported to be less than 1% but this figure may be higher in Crohn's disease or other conditions. The rate of surgical/endoscopic removal was noted to be 0.75% (Barkin, 2002).

Patients who are at increased risk of capsule retention are not appropriate study subjects including people with swallowing disorders or with known or suspected gastrointestinal obstructions, strictures or fistulas. In general, if a patient does not pass the MCC naturally through the upper GI tract due to gastroparesis, an EGD will be sufficient to retrieve the capsule. Given that all study patients will receive an EGD as part of their standard work-up for the disease, this does not pose a significant increased risk. Any patient with dysphagia will be excluded because a retained capsule in the esophagus is at risk of aspiration.

Patients will be advised not to have an MRI for 30 days. For patients who are unsure whether they excreted the MCC, *an abdominal X-Ray or "Navicam capsule locator" may be required as an outpatient to confirm passage.*

In order to maximize safety for all study subjects, only consented and enrolled subjects will be administered the MCC under the supervision of a physician and a sub-investigator/trained research associate responsible to the PI. In addition, the MCC will be stored in a secure, limited access area. Product accountability log must include the ¹² protocol number, investigative site name, product name, medical units (i.e., capsules), serial number and subject ID number.

We believe the study poses a low privacy risk to subjects as all data will be encrypted and no PHI will be stored with data. Data will be stored in a REDCap database that allows for the common collection of data from multiple sites.

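### Section 10.4.2 bars all staff contact after a participant withdraws, with no exception for a swallowed capsule not yet known to have passed

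*Protocol*

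**What the plan says.** On withdrawal by the participant, Section 10.4.2 is unconditional: "If subject withdraws from the study, no further contact will be attempted or made by study staff". Section 10.4.1 lets a participant leave at any time and for any reason, and adds: "Subject should provide written notice to PI as to withdrawal intent". The rule therefore deals with formal withdrawal, not with missed calls.

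The protocol's means of safety follow-up lie elsewhere:

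- Section 8.3.7 puts the question about noticing the capsule pass in the Day 7 and Day 30 forms.
- Section 9.4 checks adverse events at the same two time points. Its sentence on the calls also says that "chart review is only performed if person is lost to follow-up will be conducted to check for symptom resolution and adverse events". The wording is garbled, but the research summary in the same section confirms that chart review is for those lost to follow-up.
- Section 6.3.1 adds a conditional check. "For patients who are unsure whether they excreted the MCC", an abdominal X-ray or the capsule locator may be required. It also says: "Patients will be advised not to have an MRI for 30 days".
- Section 6.3.1 lists retention in the small bowel among the potential major adverse events.
- Sections 7.2 and 8.2 make 30-day safety a secondary objective and outcome.

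**The concern.** Consent is signed and the capsule swallowed on the same day (Section 9.4, Day 0). Any withdrawal after that visit but before passage is known leaves a person who may still carry the device. From then on staff may not ask whether it has passed, and so may not find out that the person is unsure and could need the X-ray or locator. The participant also has no stated way to leave some parts of the study, such as the questionnaires, while keeping a safety call.

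What is at stake is safety ascertainment for single individuals, and a 30-day safety report that may be incomplete for people exposed to the device. Section 13.2 plans no formal inference, so no test, power figure or estimate of visualization depends on this.

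**Working it through.** **Reading the rules together**

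1. Can withdrawal follow ingestion? Yes: Section 10.4.1 allows it at any time.
2. How does the study learn about capsule passage? By asking on Day 7 and Day 30 (Section 8.3.7). Section 10.4.2 stops this after withdrawal.
3. How does it learn about adverse events to Day 30? Through the same contacts (Section 9.4), which are also stopped.
4. Does chart review fill the gap? It is not contact, so Section 10.4.2 does not itself forbid it. But Section 9.4 limits it to people lost to follow-up, and someone who has given written notice is not described that way.
5. Does the X-ray or locator fill the gap? Only if staff learn that the person is unsure, which depends on step 2.
6. Does the EGD fill the gap? In part. Section 6.3.1 relies on it for a capsule held up in the stomach, not in the small bowel. It may also come first, because the protocol "will allow MCC procedure to be performed up to 14 days either before or after an EGD".

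**Size**

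The protocol gives no figure for this point, so there is none to reproduce. Inputs:

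- Retention: Section 6.3.1 says "The incidence of capsule retention has been reported to be less than 1" percent, so p < 0.01. The same section says "The rate of surgical/endoscopic removal was noted to be 0.75" percent, but that is a removal rate and is not used here.
- k, the number who withdraw after swallowing and before passage is known: not in the protocol. The values 1, 3 and 5 are illustrative.
- Assumption: withdrawers have the same retention risk as other participants.

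Expected retained capsules among k people: k × p, so fewer than 0.01 per person.

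Chance of at least one: 1 − (1 − p)^k.

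| k | Expected, below | Chance of at least one, below |
|---|---|---|
| 1 | 0.01 | 1 − 0.99 = 1.0% |
| 3 | 0.03 | 1 − 0.99³ = 1 − 0.9703 = 3.0% |
| 5 | 0.05 | 1 − 0.99⁵ = 1 − 0.9510 = 4.9% |

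As a wider range, suppose that 5% to 20% of the 72 participants withdrew in this window (also an assumption). That is 72 × 0.05 = 3.6 to 72 × 0.20 = 14.4 people, with fewer than 0.036 to 0.144 expected retained capsules.

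These are ceilings. Section 10.2 excludes Crohn's disease, gastroparesis, suspected obstruction and anatomy-changing surgery, so the true figures are probably lower. Missing data do not depend on p: each such withdrawal may cost one participant's 30-day safety record, or 1/72 = 1.4% if all 72 swallow a capsule.

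**The case against.** The strongest reply is that the rule simply honours a formal, often written, withdrawal. No section promises contact afterwards, so nothing is contradicted. That is fair, and it shapes the remedy: a safety contact should be offered, not continued by default. It does not defend a rule that gives no chance to accept one.

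The second reply is that safeguards remain. The PI is available to participants 24 hours a day and participants are told to return if concerning signs develop. The EGD is standard of care, normally follows the capsule, ideally within 5 days, and is not cancelled by leaving the study. Section 19.1 has participation noted in the medical record, so treating clinicians can see it. All of this stands and makes the gap smaller. But these routes rely on the participant or an outside clinician noticing a problem, and Section 6.3.1 itself reports that a retained capsule is often without symptoms or leads to a diagnosis.

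Third, confirming capsule passage is not systematic for anyone, and the consent pages, which are not shown, may contain a safety clause. Both are true. A consent clause allowing contact would still conflict with Section 10.4.2 as worded.

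A reader might also infer more than the text supports:

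- *Participants withdrawn by the PI lose safety follow-up too.* Section 10.4.2 only adds a notification for them. It does not bar contact or say that their calls stop.
- *The rule removes a repeat MRI warning.* No repeat is scheduled for anyone, and withdrawal does not undo advice already given.
- *Retention across all 72 participants measures the problem.* It would do so only if everyone withdrew after swallowing.

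**Conclusion.** The point holds in a limited form. After a withdrawal by the participant, Section 10.4.2 as written stops the contacts through which the study would learn capsule passage and 30-day adverse events, and it makes no exception for a capsule that may still be inside. The study may therefore not learn these outcomes for that person. It is not certain to miss them, because other routes could bring the information in.

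The size is very small: fewer than 0.01 expected retained capsules per such withdrawal. This rests on the protocol's stated ceiling for retention and on equal risk in withdrawers. The number of such withdrawals is unknown. No direction of bias is claimed. This is an optional improvement to a stated rule, worth making because it is cheap.

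**What to change.** Add to Section 10.4.2 wording such as: a participant who withdraws after swallowing the capsule is asked, when the withdrawal notice is received, whether they agree to (a) a check of capsule passage, with X-ray or locator if unsure, and (b) an adverse event call or chart review at Day 30. They are reminded of the 30-day MRI restriction at that point. If they decline, no further contact is made.

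Report 30-day safety on everyone who swallowed a capsule, with unknown capsule passage shown as a separate category.

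The cost is one paragraph, possibly matching consent wording, a slightly longer withdrawal conversation and a few extra calls. The notice to the PI already gives a natural moment to ask, and the existing forms (Magnet 7, 8 and 9) can record the answers. A full refusal is still respected, so some outcomes may stay unknown.
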